8.3. Tertiary/Exploratory Efficacy Analysis

Plasma and imaging biomarkers that are collected repeatedly post-baseline will be analyzed with

Version 1.0 | 28-Feb-2025 Page 28 of 56

the MMRM analysis as described above.

CSF and imaging biomarkers that are collected only at screening/baseline and Week 76 ET/ED will be analyzed using ANCOVA with a model that includes treatment group, pooled site, and baseline MMSE.

8.4. Subgroup Analyses of Efficacy Variables

The co-primary endpoints and iADRS will be analyzed in a subset of the mITT analysis set, termed the "amnestic subset", in which the following additional restrictions are applied: baseline CDR global score ≥ 1 and baseline score on the CDR memory domain ≥ 1 .

The co-primary endpoints and iADRS will be analyzed in the ITT analysis set by baseline severity, with subgroups defined as screening MMSE \geq 21 and \leq 27 versus MMSE < 21. An additional subgroup analysis for the co-primary endpoints and the iADRS will use screening MMSE \geq 20 and \leq 27 versus MMSE < 20. For these analyses, an MMRM model as previously described will be used, except that the model will have additional fixed effects for subgroup and its two-way interactions with treatment and Visit, and the 3-way subgroup-by-treatment-by-Visit interaction; and, baseline scores for the endpoint being analyzed and baseline MMSE and their interactions with Visit will be removed from the model due to their possible confounding with subgroup. Specifically, the analysis will include the categorical, fixed effects of treatment group, subgroup, pooled site, and Visit, along with the two-way interactions of treatment group with Visit and subgroup with Visit, and the three-way treatment group, subgroup, Visit interaction.

[figure not shown]
Similar models will be used to analyze subgroups by age (defined as < 65, 65-74 or ≥ 75), sex (defined as male or female), ethnicity (categories defined per FDA Guidance), race, ApoE4 genotype (defined as APOE4 non-carrier, carrier or homozygous) and medication use (cognitive enhancers, defined as yes or no).

There will be two additional subgroup analyses for the NPI-10. The first will include participants with a baseline NPI-10 score ≥ 2 . The second will analyze the agitation/aggression domain scores in participants with a non-zero baseline score in that domain.

Note that there will be two sets of results for the mild subgroup. In section 8.2 the mild subgroup analyses are conducted by applying the primary analysis model to the ITT-mild analysis set. Those analyses are the primary means of drawing inference for the mild subgroup. The subgroup analyses described here for the mild / moderate subgroups are the primary means of drawing inference for differential efficacy between the subgroups. The analyses specified in section 8.2 are the primary means of understanding efficacy within the mild subgroup because that approach allows for including the same model as other secondary and primary endpoints.

In addition, subgroup analyses will be conducted by baseline severity and baseline plasma P-tau181 level. Baseline severity will be defined by iADRS, a composite of ADAS-Cog12 and ADCS-ADL. Each participant will be categorized as high, medium, or low baseline severity by dividing the baseline iADRS scores into tertiles. Baseline P-tau181 will be defined as high or low based on a median split. The 4-way interaction between baseline composite severity category, baseline P-tau category, Visit, and Treatment will be fit in an MMRM model to assess the changes over time by treatment within the six categories defined by the baseline composite and baseline P-tau categories. Within-patient errors will be modeled as described for the primary analysis.

Version 1.0 | 28-Feb-2025 Page 29 of 56

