2.2. Sample Size and Power

The sample size for this study was originally determined as follows.

Planned enrollment was approximately 1083 participants with mild-to-moderate AD. The sample size was determined by a power analysis of ADAS-Cog using data from a similar population over 76 weeks. This analysis determined that the comparison between an active arm and placebo requires group sizes of 289 to provide 90% power to detect a 45% difference from placebo at 76 weeks, based on the use of a two-sided test at the alpha = 0.05 significance level. The power calculation assumes a true mean change from baseline for placebo of 6.0 points and a standard deviation of 10.0 points. Assuming a drop-out of 20%, each treatment group should enroll approximately 361 participants.

Learnings from analyses of the sister study, and results from other development programs in AD led to change in the primary analysis population for this study to include in the primary analysis only those participants with >= 44 pg/ml P-tau181 at baseline, or other confirmation of amyloid pathology (e.g., amyloid PET). Based on results of study PTI-125-07, it is anticipated that the reduction in sample size will be offset by an increase in treatment effect such that the study will have at least as much power as originally planned.

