6.1.2. Adjustments for Covariates

Primary efficacy analyses will include as covariates the baseline value of the endpoint being analyzed and the MMSE baseline score, along with the interaction of these covariates with Visit. Investigative site (pooled, see section 6.1.6) will also be included as a categorical fixed effect. Covariates observed to be important in post-hoc analyses of the PTI-125-07 study will also be included in sensitivity analyses. See section 8.4 for further details.

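### SAP 8.4 drops baseline score and baseline MMSE from its MMSE-severity subgroup models, and probably from others, for a reason that does not touch the treatment contrasts; the cost is some precision, not bias

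*SAP*

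**What the plan says.** SAP section 6.1.2 sets the primary model: "Primary efficacy analyses will include as covariates the baseline value of the endpoint being analyzed and the MMSE baseline score", each also interacting with Visit. Section 8.1 repeats this.

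Section 8.4 analyses the co-primary endpoints and iADRS in the ITT set by screening MMSE, with cuts at 21 and at 20. For these models it says that "baseline scores for the endpoint being analyzed and baseline MMSE and their interactions with Visit will be removed from the model", and gives possible confounding with subgroup as the reason. The term list that follows has treatment, subgroup, pooled site, Visit and interactions, and no baseline covariate. The next paragraph begins "Similar models will be used to analyze subgroups by age" and goes on to sex, ethnicity, race, ApoE4 genotype and medication use, without listing terms again.

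Section 8.4 then assigns roles. "The subgroup analyses described here for the mild / moderate subgroups are the primary means of drawing inference for differential efficacy between the subgroups". Efficacy within mild participants is instead judged from the ITT-mild set, which is analysed with the full primary model, both covariates included. Removal is not stated for the amnestic subset, the two NPI-10 subgroups, or the four-way model of iADRS tertile by P-tau181.

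**The concern.** The quantities of interest are the treatment difference within each subgroup level and how that difference varies across levels. Both are contrasts between randomised arms. A covariate measured before randomisation may be strongly related to the subgroup, as MMSE is to an MMSE cut, and still not confound those contrasts. The overlap affects the subgroup main effect, which is not the target. For sex, race, ethnicity, ApoE4 genotype and medication use, which are not defined by the baseline scores, the stated reason is weaker still.

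The SAP does not apply its reason consistently. ITT-mild is itself defined by MMSE, yet baseline MMSE stays in its model.

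At stake is precision in an analysis that has little to spare. The mild/moderate model carries the SAP's main inference on differential efficacy. No analysis set of moderate participants is defined to which the primary model would be applied. The covariates are already collected and already coded, so the loss is avoidable.

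**Working it through.** **Inputs from SAP section 2.2.** The comparison "requires group sizes of 289 to provide 90% power to detect a 45% difference from placebo at 76 weeks", with alpha 0.05, two-sided. The calculation "assumes a true mean change from baseline for placebo of 6.0 points and a standard deviation of 10.0 points". Drop-out is put at 20%, giving about 361 enrolled per group. The SAP gives no power or precision figure for any subgroup analysis.

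**Assumed inputs, not in the documents.** R² of the two covariates for Week 76 change: 0 to 0.25. Even subgroup split: 289/2 = 144.5, taken as 145 evaluable per arm per subgroup. For the simulation: correlation of 0.7 between baseline severity and MMSE; MMSE drawn with mean 21.5 and SD 3.2, rounded and limited to 16–27; a true effect of 2.7 points in every subgroup, hence no interaction.

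**1. The plan's own figure.** Difference = 0.45 × 6.0 = 2.7 points. n = 2 × (1.960 + 1.282)² × 10² / 2.7² = 288.3, so 289 per group, as stated. 289 / 0.80 = 361.25, against about 361 stated.

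**2. Does keeping the covariates bias the contrasts?** Week 76 change was simulated with 289 per arm in two arms, 3,000 replicates per scenario, R² = 0, 0.09, 0.16 and 0.25. The subgroup was either an MMSE cut at 21 or unrelated to baseline. With and without the covariates, the mean interaction estimate lay between −0.033 and 0.028 (truth 0), the mean within-subgroup effect between −2.73 and −2.67 (truth −2.7), and the interaction type I error between 0.044 and 0.057. Neither model is biased.

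**3. Precision when the subgroup is unrelated to baseline.** Residual SD = 10√(1 − R²). Within-subgroup SE = SD × √(2/145). Interaction SE = √2 times that.

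| Model | SE inflation if dropped, 1/√(1 − R²) | Subgroup SE | Interaction SE | Power, 2.7 within subgroup | Power, 2.7 interaction |
|---|---|---|---|---|---|
| Covariates dropped | – | 1.17 | 1.66 | 63% | 37% |
| Kept, R² = 0.04 | 1.021 | 1.15 | 1.63 | 65% | 38% |
| Kept, R² = 0.09 | 1.048 | 1.12 | 1.58 | 67% | 40% |
| Kept, R² = 0.16 | 1.091 | 1.08 | 1.52 | 71% | 43% |
| Kept, R² = 0.25 | 1.155 | 1.02 | 1.44 | 76% | 47% |

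At R² = 0 nothing is lost. The inflation factors do not depend on the SD of 10; the SEs and power do.

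**4. Simulated SE inflation by type of subgroup.**

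| R² | Unrelated to baseline | MMSE cut at 21 |
|---|---|---|
| 0.09 | 4–5% | about 2% |
| 0.16 | 9–11% | 4–5% |
| 0.25 | 15–16% | 7–9% |

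The MMSE-defined subgroup loses about half as much because the subgroup term recovers part of the baseline information.

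**5. Chance baseline imbalance.** A one-SD imbalance moves an unadjusted within-subgroup estimate by √R² × 10 × √(2/145), which is 0.352 points at R² = 0.09 and 0.59 at 0.25. This is the same loss in another form: at R² = 0.09, 1.120² + 0.352² = 1.254 + 0.124 = 1.378 = 1.174².

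**Limits.** The simulation is a complete-data Week 76 model, not the seven-visit MMRM with pooled site. Actual subgroup sizes and missingness after early termination are not in the documents.

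**The case against.** The strongest case on the other side is that this is an efficiency choice in secondary analyses. The 8.4 interaction models sit outside the testing sequence in section 6.1.3, section 4.2 treats p-values from other efficacy analyses as nominal, and no success criterion depends on them. In the cut-21 model the subgroup term is the randomisation stratum, so the stratification factor remains. A gain of a few percent in SE is unlikely to change a conclusion. All of that stands and limits the importance of the point, but it is not a reason to discard covariates at hand.

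Four stronger readings are tempting and are not supported:

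- A reader might infer that every subgroup analysis loses its covariates. ITT-mild keeps them, and removal is not stated for the amnestic, NPI-10 or four-way analyses. For age, sex and the rest it rests on the word similar. That is the most natural reading, but it is not spelled out.
- A reader might infer that all these models carry the main inference on differential efficacy. Section 8.4 gives that role only to mild versus moderate.
- A reader might infer that baseline imbalance biases the results, or is a harm on top of the larger SE. The outcome is already a change score, so only the dependence of change on baseline remains. Across randomisations this is variance, already counted in the unadjusted SE.
- A reader might take the two different mild results as an error. The SAP announces both and gives each a role. They would differ even with equal covariates, because 8.4 fits site effects and covariance jointly to mild and moderate participants.

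**Conclusion.** The point holds as a loss of precision with no offsetting gain for the treatment contrasts. Removal is explicit for the MMSE cut-21 and cut-20 models and is the natural reading for age, sex, ethnicity, race, ApoE4 genotype and medication use. The stated reason concerns only the subgroup main effect.

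The size rests on an R² the documents do not supply. In the explicitly affected MMSE models the likely cost is small. Where the subgroup is unrelated to baseline, R² of 0.04 to 0.25 corresponds to 4% to 33% more participants for equal precision, from 1/(1 − R²). The loss matters most for the mild/moderate model because of its assigned role, and because power for a 2.7-point interaction is only about 37% without covariates under an even split.

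**What to change.** In section 8.4, keep the baseline endpoint score and baseline MMSE, each by Visit, in the two MMSE-cut models and in the age, sex, ethnicity, race, ApoE4 and medication-use models. Add subgroup and its interactions with treatment and Visit, including the three-way term. List the terms for each of these models so that nothing hangs on the word similar. Base inference on the treatment differences and their interaction with subgroup, and show the unadjusted model as a supplement.

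The cost is a change of SAP wording plus terms already in the primary-model code. There is one small downside. In the MMSE-defined models, displayed subgroup LS means should be evaluated at each subgroup's own baseline means, because a common overall mean would describe a baseline MMSE untypical of either group. The treatment differences do not depend on that choice, since the model has no treatment-by-covariate term.

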8.5. Responder Analyses

A responder analysis will report the number and percentage of participants in each treatment group who remain stable or show improved scores on the co-primary endpoints (analyzed separately), baseline to week 76. These analyses will be conducted for all participants, and for the mild and moderate subgroups.

A second responder analysis for the NPI-10 will report the number and percentage of participants in each treatment group with a score of 0 at baseline and these numbers and percentages with a score of 0 again at week 76. This analysis will also be conducted for mild and moderate subgroups.

The significance of the difference between treatments in response rates will be assessed using the Cochran-Mantel-Haenszel (CMH) test in all participants, stratified by mild / moderate disease status; and the difference in response rates within disease subgroups will be assessed using the CMH test stratified by ApoE4 carrier status.

8.6. Disease Progression Analyses

A progression analysis will report the number and percentage of participants in each treatment group who entered the study with mild disease at baseline (MMSE 21-27) and who then progress to moderate or to more severe disease (MMSE 16-20 and MMSE <16, respectively) by week 76.

A second progression analysis will report the number and percentage of participants in each treatment group who entered the study with moderate disease at baseline (MMSE 16-20) and who then progressed to more severe disease (MMSE <16) by week 76.

The significance of the difference between treatments in the rate of disease progression will be assessed using the CMH test in all participants, stratified by mild / moderate disease status; and the difference in progression rate within disease subgroups will be assessed using the CMH test stratified by ApoE4 carrier status.

[figure not shown]

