2.4. Treatments Administered

Participants were randomized in a 1:1:1 ratio to:

- simufilam 50 mg tablets BID, or
- simufilam 100 mg tablets BID, or
- placebo tablets BID.

The randomization was stratified by baseline low or high MMSE score (16-20 vs. 21-27).

[figure not shown]

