4.2. Introduction

Data processing, tabulation of descriptive statistics, calculation of inferential statistics, and

Version 1.0 | 28-Feb-2025 Page 17 of 56

graphical representations will use SAS (release 9.4 or higher). If the use of other software is required, the final clinical study report will specify the software that was used.

In general, summaries will be provided by study treatment group, unless otherwise noted. The column headings for the summaries will include the randomized treatment groups (Placebo BID, Simufilam 50 mg BID, Simufilam 100 mg BID), unless otherwise noted.

Continuous (quantitative) variable summaries will include the number of participants with non-missing values (n), mean, 2-sided 95% confidence interval (CI), standard deviation (SD) and/or standard error (SE) if applicable, median, and minimum and maximum values.

Categorical (qualitative) variable summaries will include the frequency and percentage of participants who are in the category for each possible value. In general, the denominator for the percentage calculation will be based upon the total number of participants in the study population for the treatment groups (or cohorts) unless otherwise specified.

The minimum and maximum will be reported with the same degree of precision (i.e., the same number of decimal places) as the observed data. Measures of location (mean and median) and bounds of CIs will be reported to 1 degree of precision more than the observed data and measures of spread (SD and SE) will be reported to 2 degrees of precision more than the observed data. Percentages will be presented to 1 decimal place.

Statistical testing and inference methods for safety and efficacy analyses are described below. Efficacy results will be considered statistically significant after consideration of the strategy for controlling the Type 1 error as described in Section 6.1.2 of this SAP. Nominal p-values may be computed for other efficacy analyses as a measure of the association between the endpoint and the treatment effect rather than formal tests of hypotheses. Unless otherwise stated, all statistical tests will be conducted at the alpha = 0.05 (two-sided) level, and a difference resulting in a p- value of ≤ 0.05 will be considered statistically significant. Corresponding 95% two-sided CIs will be presented for statistical tests.

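### The MMSE progression tests in SAP 8.6 leave out the baseline MMSE score within each severity band, which costs supportive tests roughly 1 to 8 points of power

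*SAP*

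**What the plan says.** SAP 8.6 defines two progression outcomes at Week 76 by fixed MMSE cut-offs. Participants starting at 21-27 progress if they fall into the 16-20 range or lower. Those starting at 16-20 progress if they fall below 16. For the overall comparison, "The significance of the difference between treatments in the rate of disease progression will be assessed using the CMH test in all participants"; the two severity bands serve as the strata. For the separate bands, the difference "within disease subgroups will be assessed using the CMH test stratified by ApoE4 carrier status". No other baseline variable enters either test.

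Elsewhere the SAP does use the score. Section 6.1.1 takes the screening MMSE as the baseline value. Sections 6.1.2 and 8.1 put baseline MMSE into the co-primary model as a continuous covariate, and section 8.2 does the same for MMSE change. Randomisation was stratified on the same two MMSE bands (SAP 2.4). The progression tests are not in the gatekeeping order of SAP 6.1.3. Under SAP 4.2, unless otherwise stated, "all statistical tests will be conducted at the alpha = 0.05 (two-sided) level".

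**The concern.** With a fixed cut-off, distance from it at entry is a strong predictor of crossing it. A participant who enters at 21 progresses on a 1-point loss, and one who enters at 27 must lose 7. In the moderate band the range is 1 point from 16 to 5 points from 20. The band itself carries little of this information, because the distance starts again from one point at 21.

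Two things follow. The planned tests leave predictable variation in the error, so they have less power than the collected data allow. And because randomisation was stratified on the band only, the arms can differ by chance in mean MMSE inside a band, with nothing in the test to correct for it. At stake is the precision of a supportive result that is easy to read and likely to be cited.

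**Working it through.** **The plan's own figure.** The only sizing in the documents is for ADAS-Cog: it "requires group sizes of 289 to provide 90% power to detect a 45% difference from placebo at 76 weeks", assuming "a true mean change from baseline for placebo of 6.0 points and a standard deviation of 10.0 points" (SAP 2.2).
- Effect: 0.45 × 6.0 = 2.7 points.
- n per group = 2 × (1.960 + 1.282)² × 10² / 2.7² = 288.3, so 289; power at 289 is 0.901.
- Dropout: 289 / 0.80 = 361.25, stated as 361; 3 × 361 = 1,083.

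The figure reproduces. No rate or power is stated for the progression tests.

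**Assumptions, not in the documents.** Placebo MMSE decline 2 to 4 points; SD of change 3 to 4.5; slowing 25% or 45%; baseline MMSE uniform, or peaked near 21.5; ApoE4 unrelated to progression. All-participants comparison: 289 per arm, one active arm against placebo. Mild band: 170 per arm, close to 289 × 7/12 = 169.

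**How far the starting score drives the outcome.** With whole-point scores, the progression probability is Φ((c + 0.5 − b + d) / s), where b is baseline, d decline, s the SD and c the highest score counted as progression (20 or 15). With d = 3 and s = 3.5:
- from 21: Φ(2.5/3.5) = 76%
- from 24: Φ(−0.5/3.5) = 44%
- from 27: Φ(−3.5/3.5) = 16%
- from 16: Φ(2.5/3.5) = 76%
- from 20: Φ(−1.5/3.5) = 33%

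**Power.** Simulation, 2,000 trials per scenario, uniform baseline. Each cell shows the planned CMH, then CMH stratified by MMSE point, in per cent.

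| Decline, SD | Slowing | All participants | Mild band |
|---|---|---|---|
| 2, 3 | 45% | 67.6 → 75.6 | 41.2 → 48.7 |
| 2, 3 | 25% | 25.8 → 29.3 | 15.2 → 18.0 |
| 3, 3.5 | 45% | 90.9 → 93.2 | 67.7 → 75.2 |
| 3, 3.5 | 25% | 45.0 → 50.2 | 25.9 → 28.8 |
| 4, 4 | 45% | 97.6 → 98.2 | 83.7 → 88.5 |
| 4, 4 | 25% | 58.0 → 63.0 | 37.6 → 42.9 |
| 3, 4.5 | 45% | 76.3 → 78.5 | 50.8 → 55.1 |
| 3, 4.5 | 25% | 31.2 → 33.4 | 19.5 → 21.5 |

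Gains are about 1 to 8 points overall and 2 to 8 in the mild band. The peaked baseline, run for all participants, gives about 1 to 5. Relative efficiency, the squared ratio of the mean z-statistics, is 1.05 to 1.18 overall and 1.11 to 1.22 in the mild band. Crossing MMSE point with ApoE4 changes the mild-band power by about 1 point at most.

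**Cross-check with logistic regression.** Mild band, 150 per arm, decline 3.5, with ApoE4 and baseline MMSE in the model. At 45% slowing, power rises from 82% to 90% (SD 3) and from 66% to 72% (SD 4). At 30% slowing it rises from 50% to 59% and from 36% to 40%.

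**No treatment effect.** Mild band, 12,000 trials per scenario.
- Overall type I error: 4.8-4.9% as planned, 4.6-5.1% by MMSE point.
- A uniform 21-27 baseline has variance (49 − 1)/12 = 4, so the difference between arm means has SD 2 × √(2/170) = 0.217. A difference of 0.35 or more in either direction then arises in about 11% of trials.
- In those trials the planned test rejects 10-12% of the time, against 4-5% by MMSE point. Logistic-regression runs gave 5-7%.
- The progression rate shifts by 8.5 to 10.7 percentage points per MMSE point of imbalance, so 0.35 points moves it by 0.35 × 8.5 to 0.35 × 10.7, or 3.0 to 3.7 points.

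**The case against.** The case for leaving the plan alone is that CMH is valid and conventional here, and its result sits directly beside the raw percentages. SAP 8.2 already gives a baseline-adjusted analysis of MMSE change, and SAP 8.4 names the 8.2 analyses as the main basis for inference in the mild group. The progression tests are outside the testing hierarchy, and SAP 4.2 lets p-values for other efficacy analyses be read as nominal. All of that stands, and it limits the importance of the point. It does not explain why the covariate is dropped for the outcome defined by distance from an MMSE cut-off.

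The numbers rest on assumed MMSE inputs. The trial also stopped early, so Week 76 counts may be well below 289 per arm. That is a fair limit on the size of the gain, though not on its direction in these scenarios.

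Three stronger readings are tempting, and the documents do not support them.
- A reader might infer that baseline MMSE is ignored altogether. The all-participants test and the randomisation both use the band; only position within it is left out.
- A reader might extend the point to the responder tests in SAP 8.5. Those use neither MMSE nor one fixed score for everyone. The co-primary responders are judged against their own baseline, and the NPI-10 analysis concerns a score of 0 at both times, so its baseline is constant if the rate is taken among those starting at 0. On the SAP's own ADAS-Cog inputs, response is Φ(−6.0/10) = 27.4% on placebo and Φ(−3.3/10) = 37.1% on active, with power about 70% at 289 per arm. Adjusting for baseline changes that by −1 to +3 points for assumed baseline-change correlations of 0 to 0.4.
- A reader might infer that the tests are invalid. Averaged over randomisations, type I error is about 5% with either method.

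**Conclusion.** The point holds for the MMSE progression tests in SAP 8.6, as a loss of efficiency and a lack of protection against chance imbalance within a band. In the main grid the loss is about 1 to 8 percentage points of power; one cell of the logistic cross-check reached 9. In relative efficiency, adjustment is worth about 5 to 18% more participants overall and 11 to 22% more in the mild band. These figures depend on the assumed decline, SD, baseline distribution and group sizes. That a fixed cut-off makes the starting score matter follows from the definition of progression itself. The co-primary conclusion is unaffected. This is a minor, inexpensive improvement.

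**What to change.** Change SAP 8.6 only, while the data are still blinded. Test progression by logistic regression with treatment, continuous baseline MMSE and the stratum already planned: the mild/moderate band in all participants, ApoE4 carrier status within each band. The band term must stay in the overall model so that risk can restart at 21. With it, a linear MMSE term is equivalent to points above the cut-off, since (MMSE − 16) and (MMSE − 21) differ only by the constant 5. CMH stratified by baseline MMSE point is an acceptable alternative. Report the covariate-standardised risk difference with its 95% confidence interval, and keep the planned CMH as a supportive line.

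The cost is a few lines of SAP text and one procedure call, with no new data. The downside is that a standardised difference must be shown and explained beside the raw percentages. SAP 8.5 needs no change on this account. In the same edit, reconcile the progression tables in SAP 13.2, which carry ADAS-Cog 12 and ADCS-ADL titles although 8.6 defines progression on MMSE.
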